1.3. The clinical reason for conducting this non-interventional study

ZOLEDRONIC ACID ACTAVIS is a generic formulation containing the active substance zoledronic acid monohydrate the first time used in the Polish population. This formulation obtained the registration in January 2013 and is available in commercially pharmacy, and its indications include the treatment of:

- prevention of skeletal related events (patholological fractures, spinal compression, radiation or surgery to bone, or tumor--induced hypercalcaemia) in adults patients with advanced malignancy involving bone,

- treatment of adult patients with tumor-induced hypercalcaemia (TIH).

It should be emphasized that the treatment with Zoledronic acid Actavis formulation in the prevention of skeletal complications in patients with advanced malignancies involving bone is a long process, therefore not only to minimize the symptoms of the disease, but also a good tolerance and acceptance of the therapy by the patient are important. Moreover, the use of zoledronic acid requires constant security monitoring.

2. THE AIM OF THE STUDY

2.1. The main aim of the study:

Assessment of safety profile of ZOLEDRONIC ACID ACTAVIS in patients with advanced malignancy involving bone.

2.2. The additional aim of the study:

Assessment of the tolerance of the treatment.

3. STUDY DESIGN

3.1. Basic information

This is a non-interventional, post-marketing study. This study collects data on the occurrence of any adverse events and tolerability of **ZOLEDRONIC ACID ACTAVIS** formulation during treatment of patients **WITH ADVANCED MALI-GNANCY INVOLVING BONE**. Treatment with this preparation should follow the instructions specified in the Summary of Product Characteristics. Patient inclusion of the study is independent of the previous decision regarding the treatment of the patient with **ZOLEDRONIC ACID ACTAVIS** formulation.

3.1.1. Characteristics of the study population

Adult patients of both sexes, who, based on ICD-10 meet the criteria for diagnosis of advanced malignancy involving bone and do not meet the exclusion criteria, as well as treated with ZOLEDRONIC ACID ACTAVIS not less than 30 days prior to enrollment will be included to the study.

3.1.2. Study design

This project is post-marketing, non-interventional, open multicenter study.

3.2. Endpoints

Endpoints of safety- data collection of related adverse events associated with therapy.

3.3. Substantiation of the study construction

Non-interventional, post-marketing study assessing the safety of treatment with **ZOLEDRONIC ACID ACTAVIS**. In study patients no additional diagnostic procedures or monitoring and analysis will be performed and in analysis of the collected data, epidemiological methods only, will be used.

The aim of the study is to collect data on any adverse events that may occur during the routine use of ZOLEDRO-NIC ACID ACTAVIS in the Polish population, according to the indications and other information contained in the Summary of Product Characteristics.

The study will be conducted in approximately 3,500 patients who were treated with a ZOLEDRONIC ACID ACTAVIS formulation as part of routine therapy. Observation of the safety using the study drug by one patient will last for four months due to the chronic nature of the therapy. During this time, centers will gather data on any adverse events of ZOLEDRONIC ACID ACTAVIS that will be recorded in Observation Form and reported to the company Europharma M. Rachtan Sp. z o.o. Please see section 9.

3.3.1. Duration of the study

Observation of patients during the study will take approximately four months from the date of first visit.

4. COMPLIANCE WITH TERMS OF GOOD CLINICAL PRACTICE, ETHICAL ISSUES AND INFORMED CONSENT TO PARTICIPATE IN THE STUDY

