| DESIGN OF THE STUDY: | In the study will participated Oncologist and Urologist proving treatment of patients with advanced malignancies involving bone using ZOLEDRONIC ACID ACTAVIS formulation not less than 30 days prior to enrollment. Observing program will be implemented about 4 months. Data on the safety profile of ZOLEDRONIC ACID ACTAVIS formulation will be recorded in individual observation form (CRF) over two consecutive visits: the starting visit (first -1) and control visit (second -2) at least two months from the date of 1st visit. According to the date of the planned visit arising from clinical needs of the patient. |
| STUDY POPULATION: | Adults patients diagnosed with advanced malignancies involving bone (diagnosis according to ICD-10) in which by clinical indications at least 30 days prior to enrollment started therapy with ZOLEDRONIC ACID ACTAVIS formulation. |
| DRUG ASSESSED IN THE NON-INTERVEN- TIONAL STUDY: | ZOLEDRONIC ACID ACTAVIS 4 mg/5mL concentrate for solution for infusion contains in 1 mL concentrate 0.8 mg zoledronic acid (as monohydrate). It is sterile, clear and colorless concentration for solution for infusion. ZOLEDRONIC ACID ACTAVIS formulation indicated in prevention of skeletal related events (pathological fractures, spinal compression, radiation or surgery to bone, or tumor-induced hypercalcaemia) in adults patients with advanced malignancies involving bone as well as in treatment of adults patients with tumor-induced hypercalcaemia (TIH). |
| ENDPOINTS: | Safety endpoints and methods its evaluation: Collection of information on adverse events related to ZOLEDRONIC ACID ACTAVIS formulation treatment. Serious adverse events should be reported to EUROPHARMA immediately, not later than 24 hours after being informed of the SAE. This report does not relieve the doctor from the notification of adverse events in accordance with Art. 45a of the Act on the profession of doctor and dentist. |
| STATISTICAL METHODS: | A sample size of approximately 3,500 patients was based on the feasibility study. The data analysis obtained in the study will be descriptive: data sets will consist of summary statistics, such as numbers, mean values, standard deviation, median, minimum and maximum values observed frequency/ percentage. The safety analysis will be conducted on the safety population. |
| | |

| Procedures for particular visits | | Visit 2* |
|--|---|----------|
| Demographic data | х | |
| Data on the primary disease | х | |

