6. METHODOLOGY

6.1 Schedule of the study

Summary of observations and assessments in the implementation of this study are presented in the following table.

Table1. Schedule of the project

| Procedures for particular visits | Visit 1 | Visit 2* |
|--|---------|----------|
| Demographic data | Х | |
| Data on the primary disease | Х | |
| Qualification of patient to the non-interventional study (inclusion criteria) | Х | |
| History concerning the treatment of the primary disease before the administration of ZOLEDRONIC ACID ACTAVIS formulation | Х | |
| History concerning comorbidities and its treatment | Х | Х |
| History concerning course of treatment and the occurrence of possible adverse events of ZOLE- DRONIC ACID ACTAVIS formulation | Х | Х |
| History concerning tolerance of ZOLEDRONIC ACID ACTAVIS formulation in patient opinion | Х | Х |
| Recording of any changes in the drugs used in comorbidities therapy during treatment with ZOLE- DRONIC ACID ACTAVIS formulation | Х | Х |

* This visit will take place only if it is planned as a part of routine observation of the patient.

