6.2 Visits to a specialist clinic under the study

6.2.1 Screening visit (day 0, visit 1)

All patients will use ZOLEDRONIC ACID ACTAVIS in accordance with the decision of the treating physician and in accordance with the conditions contained in the Summary of Product Characteristics. In the Observation Form the following information will be recorded:

- » patient number
- » patient initials
- demographic data
- » data on primary disease
- » data on treatment with ZOLEDRONIC ACID ACTAVIS
- » concomitant diseases on the basis of medical history
- » data on pharmacotherapy of concomitant diseases
- » determination of the inclusion and exclusion criteria
- » data on tolerance of treatment with ZOLEDRONIC ACID ACTAVIS in opinion of the patient
- » data on adverse events related to treatment with **ZOLEDRONIC ACID ACTAVIS**.

6.2.2 Control visit 2 at least two months from the date of 1st visit according to the date of the planned visit arising from clinical needs of the patient

Patients will be reported on visits to the center for a set period of time. These visits will be conducted in accordance with the plan as part of routine follow-up of the Patient and time set according to the individual clinical needs. During these visits, the Investigators will collect and recorded in the Observation Form (CRF) information on the current course of the primary disease, its current treatment, adverse events related to treatment with ZOLEDRONIC ACID ACTAVIS, potential changes of pharmacotherapy used in primary disease and concomitant disease treatment and assessment of tolerance treatment with ZOLEDRONIC ACID ACTAVIS in the opinion of the patient.

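### The protocol states about four months of safety observation per patient, but its visit schedule does not secure it

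*Protocol*

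**What the plan says.** Two sections of the Protocol give a length of observation for each patient. Section 3.3 gives it with a reason: "Observation of the safety using the study drug by one patient will last for four months due to the chronic nature of the therapy". Section 3.3.1 repeats it: "Observation of patients during the study will take approximately four months from the date of first visit".

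The schedule is set elsewhere. The synopsis (Design of the study) describes a "control visit (second -2) at least two months from the date of 1st visit", and section 6.2.2 has "Control visit 2 at least two months from the date of 1st visit according to the date of the planned visit arising from clinical needs". Neither gives a latest date. The footnote to the visit table, in the synopsis and in section 6.1, adds: "This visit will take place only if it is planned as a part of routine observation of the patient". Section 7.2 accordingly allows for one visit or two. Section 7.1.2 says event information is obtained at clinic visits by direct questioning. No contact at month four is defined.

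The synopsis also says "Observing program will be implemented about 4 months", after introducing the term as its name for the study. It does not say whether this is calendar time or time per patient. No enrolment period is given anywhere.

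**The concern.** The stated period and the schedule do not match. A reader of sections 3.3 and 3.3.1 would take each patient to have been followed for about four months. Under sections 6.1, 6.2.2 and 7.2, a patient can complete the study with no contact after Visit 1, or with one at two months, and still be fully compliant.

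This affects what the results describe. Section 10.4 plans event frequencies in the study population, and section 10.4.3 tabulates events in the safety population, which section 10.2 defines as everyone who received at least one dose. Patients with no follow-up, two months or longer therefore share one denominator, while the text describes it as four months. A frequency with unstated and unequal observation time cannot be compared with another source, and non-serious events would tend to be under-counted relative to a true four-month follow-up.

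**Working it through.** There is no powered sample size to reproduce: section 10.3 says the number was set by practical limits. The check is timeline arithmetic.

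**Inputs from the Protocol.** About 3,500 patients (section 10.3); 4 months stated per patient (sections 3.3 and 3.3.1); Visit 2 no earlier than 2 months, with no maximum (synopsis, section 6.2.2); Visit 2 conditional on routine planning (section 6.1); about 4 months for the programme (synopsis).

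**Inputs assumed, because the Protocol gives none.** The share *s* of patients with a Visit 2, its timing *t* in months, and an enrolment period of *A* months with uniform enrolment.

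**Step 1: what the stated period implies.** 3,500 × 4 = 14,000 patient-months after Visit 1.

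**Step 2: what the schedule covers.** Scheduled observation for one patient is the date of the last visit minus the date of Visit 1: 0 months with no Visit 2, 2 months at the earliest Visit 2, and 4 or more only if Visit 2 falls at month four or later. Over the cohort it is 3,500 × *s* × *t*:

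| Share with Visit 2 | Timing (months) | Patient-months | Of 14,000 |
|---|---|---|---|
| 100% | 2 | 7,000 | 50% |
| 100% | 3 | 10,500 | 75% |
| 100% | 4 | 14,000 | 100% |
| 80% | 3 | 8,400 | 60% |
| 50% | 2 | 3,500 | 25% |

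The stated period is met on average only if the product of share and timing reaches 4 months. Nothing in the schedule requires this.

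**Step 3: the synopsis sentence, if it means calendar time.** A patient enrolled *u* months after the start can be followed for at most 4 − *u* months. The mean possible follow-up is 4 − *A*/2, and the share able to reach a Visit 2 at two months is min(1, 2/*A*). Giving everyone four months would need a calendar length of *A* + 4.

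| Enrolment *A* (months) | Mean possible follow-up (months) | Can reach month 2 | Patients | Calendar length needed (months) |
|---|---|---|---|---|
| 1 | 3.5 | 100% | 3,500 | 5 |
| 2 | 3.0 | 100% | 3,500 | 6 |
| 3 | 2.5 | 67% | 2,333 | 7 |
| 4 | 2.0 | 50% | 1,750 | 8 |

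**Step 4: the same sentence, if it means time per patient.** It then agrees with sections 3.3 and 3.3.1, and Step 3 does not apply. Step 2 is unaffected. The Protocol would then state no calendar length at all.

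**The case against.** The strongest reply is that four months remains possible and that safety information does not come only from Visit 2.

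- Visit 2 has no latest date, so it can fall at month four or later. This stands. A reader might infer that four-month observation cannot happen; the Protocol does not support that. It is permitted but not secured.
- Section 3.3.1, although headed as the duration of the study, gives that duration per patient from the first visit. The synopsis sentence may mean the same, and then there is no clash with programme length. This stands as one of two readings. The other also has support, because the synopsis uses the term as a name for the study. A reader might infer that at most half the patients can reach Visit 2. That needs the calendar reading and also enrolment spread over all four months; with enrolment of one or two months the share is 100%.
- Related serious events are reportable within 24 hours of the investigator learning of them, whatever the visit date (sections 9.1.1, 9.3.1 and 9.6), and section 7.1.2 asks doctors to report related events that they observe. This stands, and narrows the gap mainly to non-serious events that nobody asks about after the last visit.
- Visit 1 also collects events from before enrolment (section 7.1.2), and every patient has at least 30 days of prior treatment (section 5.2). This stands: a patient with one visit contributes data, though not observation after Visit 1. Prior treatment has no upper limit either, so an inference that late-onset events are the ones lost has no support in the Protocol.
- Section 10.3 disclaims definitive safety conclusions, and section 10.4.2 tabulates how many patients attend later visits. This softens the consequence, but attendance counts do not show how long each patient was observed.

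Section 5.1 does not close the gap: its minimum of one follow-up is worded per physician, not per patient. A separate analysis plan might define observation time, but it cannot add a contact that the schedule lacks.

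**Conclusion.** The point holds as a mismatch within the Protocol: about four months per patient is stated and used to justify the design, while the schedule guarantees no observation after Visit 1 and only two months where Visit 2 takes place at its earliest date. If all 3,500 patients attended at two months, half of the implied patient-months would be covered (7,000 of 14,000). Other figures depend on the assumed share and timing of Visit 2. The shortfall concerns mainly non-serious related events.

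The ambiguity of the synopsis sentence is a second, smaller point. Its size (mean possible follow-up of 3.5 down to 2.0 months for enrolment of 1 to 4 months) applies only on the calendar reading with uniform enrolment. The study is descriptive, so no test or power is affected; what changes is the period that the event frequencies can be said to cover.

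**What to change.** Reconcile the synopsis, sections 3.3 and 3.3.1, the visit-table footnote, and sections 6.2.2 and 7.2 in one of two ways.

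1. **Restate the period.** Describe observation as running from Visit 1 to a single routine visit two months or more later, where one takes place, and drop the four-month statement. Report event frequencies together with the actual observation time, and separately for patients with and without Visit 2. The cost is a less favourable stated period and two extra summaries.
2. **Keep four months and secure it.** Add a month-four status entry for every patient, taken from routine records with no extra visit or procedure: alive or dead, on or off the drug with the reason, and related events since the last contact. This is compatible with the non-interventional design. The cost is a short form per patient, and a longer programme if the four months in the synopsis was meant as calendar time.

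In either case, state the calendar length (enrolment period plus follow-up) separately from the time per patient.

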4.1 Compliance with terms of good clinical practice, and ethical issues

This is a non-interventional study, thus not subject to the provisions of Directive 2001/20/EC of the European Parliament and of the Council of Europe of 4 April 2001.

The study will be conducted in accordance with all applicable provisions of Polish law.

4.2 Informed consent to participate in the study

In accordance with the Polish law in the case of non-interventional studies the obtain patient written informed consent to participate in the study is not required.

5. STUDY POPULATION

5.1 Records of participants in the study

Each Investigator will be required to keep list of patients included in the study. The list shall include the Patient name, initials and date of birth and must be kept confidentially at the study center.

The study is planned to include approximately 3,500 patients by Polish Oncologists and Urologists. Each physician participating in the study should make at least one follow-up.

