5.2 Inclusion criteria

All participants of the study must meet the following criteria:

- » Adult patients with advanced malignancies with bone metastases
- » Treatment with ZOLEDRONIC ACID ACTAVIS formulation at least 30 days prior to enrollment

The inclusion of each participant in the study must be separated from the decision on the treatment with ZOLEDRO-NIC ACID ACTAVIS formulation.

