7.1 Safety endpoints and methods of its evaluation

7.1.2. Related adverse events

Data on adverse events related to treatment with **ZOLEDRONIC ACID ACTAVIS** will be collected during the observation period and will also include adverse events occurring before enrolment to the Study. Information on these events will be collected during visits to specialist clinics based on directly asked questions in the survey. Doctors are required to report observed related adverse events to [contact]. For further description on reporting of adverse events please see Section 9.

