10.3. The method of determining the sample size

This is a non-interventional study in which the number of patients about 3,500 was determined taking into account the practical limitations, and not on the basis of statistical analysis. Therefore, this study does not make up the basis for the formulation of definitive conclusions about the safety of the study drug.

This is a descriptive study evaluating safety and tolerance of treatment with study drug, thus in this study basic statistical analysis will be performed.

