10.4. Statistical methods

On the basis of reported adverse events, the frequency of their occurrence in study population will be assessed. For the most common adverse events the characteristics of subpopulation in which it was reported will be analyzed.

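### The protocol does not prevent patients being enrolled selectively on an adverse event history that is already known and counts towards the main endpoint

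*Protocol*

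**What the plan says.** **Timing of entry.** Protocol 5.2 requires "Treatment with ZOLEDRONIC ACID ACTAVIS formulation at least 30 days prior to enrollment"; 3.1.1 and 5.3 agree.

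**What counts.** Section 7.1.2 states that the data on related adverse events "will also include adverse events occurring before enrolment to the Study". Table 1 (6.1) and 6.2.1 have these events, and the patient's own view of tolerance, recorded at visit 1.

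**Who is entered.** Section 5.1: "The study is planned to include approximately 3,500 patients by Polish Oncologists and Urologists". It continues: "Each physician participating in the study should make at least one follow-up". The list it asks investigators to keep covers patients included in the study. Patient numbers follow the order of inclusion (8.3, Patients identification).

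**The separation rule.** Section 3.1: "Patient inclusion of the study is independent of the previous decision regarding the treatment". Section 5.2 repeats it: "The inclusion of each participant in the study must be separated from the decision on the treatment with" the product. Both concern the decision to treat.

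**The output.** Section 10.4: from the reported events, "the frequency of their occurrence in study population will be assessed". The main aim is the safety profile (2.1) and the additional aim is tolerance (2.2).

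**The concern.** Anyone entering a patient after a month or more of treatment can already know whether that patient reacted to the drug, and that reaction counts. The separation rule guards against prescribing for the sake of the study. It does not guard against entry that depends on how the patient has fared.

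If patients who tolerate the drug are entered more readily, the reported frequency is too low. If patients with a memorable reaction come to mind first, it is too high. The direction could differ between sites. The tolerance rating at visit 1 is exposed in the same way. Because only included patients are listed, the report could not show whether this had happened. More patients would not help, since this is bias and not sampling error.

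**Working it through.** The plan has no figure to reproduce. Section 10.3 says the number of patients "was determined taking into account the practical limitations, and not on the basis of statistical analysis", so there is no precision target or other statistical input behind 3,500.

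**Step 1: is part of the outcome known at entry?** Yes. Entry comes at least 30 days after treatment start (5.2), and earlier related events count (7.1.2). Visit 2 takes place only if routinely planned (Table 1 footnote), and 7.2 allows data from a single visit. For a one-visit patient, the recorded events are those known by visit 1.

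**Step 2: does anything break the link between that knowledge and entry?** No section sets consecutive or all-eligible entry, a sampling rule, a site quota or a log of patients passed over. Numbering in order of inclusion does not govern who is included. Consent is not required (4.2, 13.1), so the protocol describes no gate other than the physician.

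**Step 3: how large could the effect be?** This is an illustration for events already known at entry.

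Inputs:
- *N* = 3,500 (5.1, 10.3).
- *p*, the true share of eligible patients with a known related event: assumed at 10%, 1% and 0.1%, which are boundaries of the frequency classes listed in 1.2.
- *r*, the chance of entry for a patient with such an event relative to one without: assumed, 0.5 to 1.5.

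Formulas: observed = *pr* / (*pr* + 1 − *p*); 95% half-width = 1.96 × √(*p*(1 − *p*)/*N*).

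At *p* = 10%:
- *r* = 0.5: 0.05/0.95 = 5.3%
- *r* = 0.8: 0.08/0.98 = 8.2%
- *r* = 1.5: 0.15/1.05 = 14.3%
- half-width: 1.96 × √(0.09/3,500) = 0.99 points

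| True *p* | Observed, *r* = 0.5 | *r* = 0.8 | *r* = 1.5 | Half-width (points) | Shift in half-widths |
|---|---|---|---|---|---|
| 10% | 5.3% | 8.2% | 14.3% | 0.99 | −4.8, −1.85, +4.3 |
| 1% | 0.50% | 0.80% | 1.49% | 0.33 | −1.5, −0.6, +1.5 |
| 0.1% | 0.05% | 0.08% | 0.15% | 0.10 | −0.5, −0.2, +0.5 |

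For common events, even modest selection (*r* = 0.8) moves the estimate by more than its sampling error. For events near 0.1%, sampling error dominates. With all eligible patients entered, *r* = 1 and the expected frequency equals *p*; *N* is unchanged.

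**Step 4: what the illustration leaves out.** Observation runs for about four months from visit 1 (3.3, 3.3.1). Events in that time are unknown at entry, so *r* does not act on them directly. The frequency of all events would shift less than the table shows wherever first events fall after entry.

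**The case against.** The strongest reply is that the protocol nowhere gives physicians a free choice. Section 3.1.1 says patients who meet the criteria will be included, and 5.2 and 5.3 contain no criterion of investigator judgement. This stands in part: a reader might infer that physicians do pick their patients, but that comes from silence, not from text. Section 3.1.1 reads as a statement of eligibility, however. It does not oblige a site to enter everyone, and nothing would show if a site did not.

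Three other stronger readings are tempting and are not supported.
- A reader might take the sentence on at least one follow-up as a minimum of one patient per physician. It may equally mean one follow-up visit. On either reading it sets no order or quota, and the point does not rest on it.
- A reader might conclude that the study will report, say, 5.3% instead of 10%. Both *p* and *r* are assumed, and the formula covers only events known at entry.
- A reader might say that no analysis could help. Patients never listed cannot be recovered, but histories are taken separately at visits 1 and 2, so splitting events at enrolment would isolate the part less directly exposed.

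Two further replies carry less weight. Section 9.1 ties related events to the active phase of the study, but 7.1.2 expressly adds earlier ones. Section 10.3 disclaims definitive safety conclusions, which lowers the stakes. It derives that caveat from how the sample size was set, though, and so does not warn of selection.

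**Conclusion.** The gap is real and worth closing before enrolment. Followed exactly as written, the protocol allows entry to depend on an outcome that is already known and counted, and it keeps no record from which this could be detected. The event frequency and the visit 1 tolerance rating can be biased either way.

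The documents support neither a size nor a direction, and they do not show that selection will occur. Under the assumed values, a true 10% for events known at entry would appear as 5.3% to 14.3%, against a half-width of about 1.0 point. The relative effect is much the same for rarer events, but there it is small beside sampling error. An enrolment rule belongs in the protocol, so this is not a matter left to an analysis plan.

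**What to change.** Add to Protocol 5.1 that, from the site's start date until its enrolment period ends, each physician enters every eligible patient in order of attendance. Require the site to keep an anonymous count of eligible patients not entered, with the reason.

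In the report, give the enrolled-to-eligible ratio overall and by site, and tabulate events before enrolment separately from events after it.

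A count with reasons is enough. Logging clinical details of patients who are not entered would be heavier and would sit badly with 13.1, where the absence of consent is justified partly by the limited data collected.

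The cost is some logging time at sites and less freedom for physicians in whom they enter. No visit, procedure or patient is added. If compliance is imperfect, the ratio will at least make that visible.
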